Pre-visit Questionnaire to Increase Influenza Vaccinations

Study Protocol with Statistical Analysis Plan

NCT05508698

7/21/2023

Study Protocol

Scientific Background

Almost everyone ages 6 months or older can benefit from the influenza vaccine, which can reduce illnesses, missed work, hospitalizations, and death by reducing the likelihood of contracting influenza.

Objectives

The purpose of this study is to assess, prospectively, the effect on flu vaccination rates of a pre-visit questionnaire that asks patients to indicate their preferences for a flu shot at an upcoming appointment. Responses to the questionnaire are shown to clinicians via additional text in an existing flu shot alert. The investigators hypothesize that the pre-visit questionnaire will lead to increased flu vaccination compared with standard practices.

Design

This study is a randomized controlled trial with 2 study arms. Patients were pre-randomized to receive (or not receive) a one-item, pre-visit questionnaire about the flu shot. Questionnaire responses are shown to clinicians in an existing flu shot alert.

Methods

Patients were pre-randomized to two study arms in July 2022:

1. Passive Control: No change to standard of care for flu vaccines
2. Pre-visit Questionnaire: One-item questionnaire in online patient portal and additional information in the flu shot alert.

(Note that patients new to Geisinger after pre-randomization are not included in the study.)

Patients are enrolled in the study if they have a flu-shot-eligible appointment scheduled 14 days or less prior to their appointment.

Appointments are flu-shot-eligible if the appointment department administers flu shots (according to an EHR classification list) at the time the appointment questionnaire becomes available (14 days prior to the appointment for appointments scheduled 14 days or more before the appointment, or on the day the appointment is scheduled for appointments scheduled less than 14 days in advance).

For those in the passive control arm, we will retrospectively identify flu-shot-eligible appointments based on the departments and date ranges observed in the questionnaire arm. For example, if questionnaires were sent to patients in the questionnaire arm for appointments in a given department from 9/1/22–12/31/22, an appointment in that same department in that date range will be considered flu-shot-eligible for a patient in the passive control group.

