Additionally, patients are enrolled if, according to the EHR, they have not yet received a flu shot at the time the questionnaire becomes available (or at the time it would have become available for the passive control group).

Power Analysis

We expect that about 165,000 patients will be enrolled in the study (~82,500 per arm). This sample size allows 80% power to detect an increase in flu vaccination rates from 35% to 35.7% with two-tailed $\alpha = .05$ for any comparison between study arms.

Project Status

Patients were pre-randomized to their study arms in July 2022. Enrollment was complete on 4/1/23, after which the flu shot alerts were turned off across the system. Data collection continued until the primary outcome date of 4/8/23 (7 days after the final appointments). This updated version of the statistical analysis plan specifies slightly modified inclusion criteria for analysis, to correct as well as possible, and in an unbiased manner, for differences in how MyChart questionnaires were actually implemented relative to what was intended. No outcomes data were compared across study arms, and final outcomes data were not pulled or reviewed prior to uploading this document.

Statistical Analysis Plan

Planned Analyses

Primary Outcome: *Count of patients with a flu vaccination [Time Frame: Up to 21 days]*

Outcome Description: Patient received a flu vaccine (yes/no) between the day questionnaires became available for the patient's first scheduled flu-shot-eligible appointment and 7 days following the appointment. Questionnaires were available 14 days prior to the appointment date for appointments scheduled at least 14 days in advance. Questionnaires were available on the day the appointment was scheduled for appointments scheduled less than 14 days in advance.

Note that control patients did not receive a flu shot questionnaire, but they may have received other questionnaires from the health system 14 days before their appointment. We will conduct subgroup analyses for people who had responded to MyGeisinger pre-visit messages in the previous year and those who did not.

Question: Does a pre-visit questionnaire that allows patients to indicate their flu shot preferences increase the likelihood that they will get a flu shot?

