Analysis (Confirmatory): We will test the hypothesis that a pre-visit flu-shot questionnaire increases the likelihood that patients will get a flu shot. We will run an OLS regression to examine whether flu vaccination differs as a function of experimental arm.

Analysis Notes

To identify the primary analysis sample, we will limit the dataset to the first flu shot-eligible appointment for which each enrolled patient was scheduled. We will then further limit the

dataset to appointments where patients were expected to receive a questionnaire (or for those in the passive control group, where the patient would have been expected to have received a questionnaire), as defined further here:

- The appointment was in a department and entailed an encounter type that was supposed to trigger a questionnaire (even if a questionnaire was not always triggered)
- The patient was not marked as contraindicated for the flu vaccine in the flu shot BPA for the 150 days prior to the questionnaire
- The patient had a “flu shot overdue” health maintenance topic (HMT) as of two days prior to the questionnaire launch date, ensuring sufficient time for the HMT to successfully trigger the questionnaire (given that a large proportion of questionnaires were not triggered when the HMT was too recent), OR the appointment was between 9/1/22 and 9/15/22, at which time the questionnaires were triggered regardless of the HMT status

Recent work suggests that OLS regressions are appropriate in randomized experiments with binary outcome variables such as ours (Gomila, 2021).

As the treatment variation is at the individual level, we will report heteroskedasticity-robust standard errors. We will also explore the impact of clustering these standard errors at the clinic and clinic-date levels to allow for dependence across observations within these clusters. We will also investigate heterogeneity across clinics that vary along characteristics of interest, including prior-year vaccination rates.

We may run additional robustness checks. These checks may include focusing on additional inclusion/exclusion criteria (e.g., including subsequent visits with questionnaires for a given patient) and subpopulations (e.g., different visit types).

Other Pre-specified Outcomes

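### The criteria for who was expected to receive a questionnaire do not require a portal account, so unless the randomised pool was already portal-only the primary sample can include patients who could not be reached

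*Combined protocol and SAP*

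**What the plan says.** Under Methods, the questionnaire arm is described as "One-item questionnaire in online patient portal and additional information in the flu shot alert". Project Status calls these MyChart questionnaires. No paper, telephone or in-clinic route appears. The clinician-facing part depends on the same route, because Objectives states: "Responses to the questionnaire are shown to clinicians via additional text in an existing flu shot alert".

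Enrolment requires a pre-randomised existing patient, a flu-shot-eligible appointment and no flu shot recorded so far. The only stated limit on the pre-randomised pool is that "patients new to Geisinger after pre-randomization are not included in the study".

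The SAP's Analysis Notes then narrow the primary sample to "appointments where patients were expected to receive a questionnaire", with the matching would-have-been rule for controls, and define this by three criteria:

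- the department and encounter type should have triggered a questionnaire;
- no contraindication was marked in the flu-shot alert over the preceding 150 days;
- the overdue flu-shot topic was in place two days before launch, or the appointment fell between 9/1/22 and 9/15/22.

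Portal access is not among them. The nearest provision is in Planned Analyses: subgroup analyses by whether the patient had responded to pre-visit messages in the previous year.

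**The concern.** The SAP has chosen to analyse patients who would be expected to get the questionnaire, but its definition leaves out the one condition that delivery by portal makes necessary. A patient with no account who meets the three criteria counts as expected to receive it. On the route described, that patient cannot see the questionnaire and gives no response for the alert to display.

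The SAP already accepts the principle: it sets aside patients whose overdue topic was too recent because many of their questionnaires never triggered. Lack of an account is at least as direct a barrier.

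What is at stake is precision about the intended effect. Patients who cannot be exposed add variance and no effect, which pulls the estimate towards zero. Power also matters beyond the primary test, since the Other Pre-specified Outcomes are analysed only where flu vaccination differs significantly.

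**Working it through.** **Inputs from the Power Analysis section:** 35% control rate, 35.7% detectable rate, about 82,500 per arm, two-sided alpha 0.05, 80% power.

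**Assumed, not in the document:** share *q* with an active account (90% to 60%); no effect in patients without an account; the same 35% control rate with and without an account.

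**Formula** (normal approximation, equal arms of *n*): power = Φ[(d − 1.96·SE0)/SE1], where d = p2 − p1, SE0 = √[2·p̄(1−p̄)/n] and SE1 = √[(p1(1−p1) + p2(1−p2))/n].

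**1. The plan's own figure.** At 82,500 per arm and 80% power, the detectable difference is 0.659 points, a rate of 35.66%, which rounds to the stated 35.7%. Taken at exactly 35.7%, power is 84.5%. The difference is rounding; the stated figure is sound.

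**2. If 0.7 points is the effect in account holders.**

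- No portal criterion: n = 82,500 and d = 0.7*q* points. At *q* = 0.8, d = 0.56 points and SE0 ≈ SE1 ≈ 0.002353, so (0.0056 − 1.96 × 0.002353)/0.002353 = 0.42, and power is 66.3%.
- With the criterion: n = 82,500*q* and d = 0.7 points. At *q* = 0.8, n = 66,000 and SE0 ≈ SE1 ≈ 0.002632, so (0.007 − 1.96 × 0.002632)/0.002632 = 0.70, and power is 75.8%.

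| Account share | Difference, unrestricted | Power, unrestricted | n per arm, restricted | Power, restricted |
|---|---|---|---|---|
| 90% | 0.63 points | 76.3% | 74,250 | 80.5% |
| 80% | 0.56 points | 66.3% | 66,000 | 75.8% |
| 70% | 0.49 points | 54.9% | 57,750 | 70.1% |
| 60% | 0.42 points | 43.1% | 49,500 | 63.4% |

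Restriction gains power although the sample shrinks. Dilution raises the required enrolment by about 1/*q*², whereas restriction raises it by 1/*q*. At *q* = 0.8, 80% power needs 114,295 per arm unrestricted. Restricted, it needs 73,214 account holders per arm, which is 73,214/0.8 ≈ 91,518 enrolled.

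**3. If 0.7 points is the average over all enrolled patients.** Unrestricted power is 84.5% whatever the account share. At *q* = 0.8 the effect in account holders would be 0.7/0.8 = 0.875 points, and the restricted analysis with 66,000 per arm has 91.4% power.

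**The case against.** A reader might infer that the primary estimate is in fact diluted and the trial underpowered. The document does not support that. It does not describe the pre-randomised pool beyond excluding new patients, so a portal-only pool cannot be ruled out, and in that case nothing changes. The Power Analysis gives its detectable increase for the whole enrolled group, so 0.7 points can reasonably be read as an all-patient average, on which no power is missing. The 82,500 per arm is expected enrolment; the sample left after the three criteria will be smaller. All of this stands, and it makes the power table illustrative only.

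Nor is there bias between arms. The criteria apply to both, and the unrestricted comparison remains a valid effect of assignment among eligible patients. Keeping unreachable patients is a defensible pragmatic estimand, and lack of an account is a matter of reach rather than a fault in implementation. That would carry more weight if the SAP had chosen that estimand. It chose instead to analyse those expected to receive a questionnaire.

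The prior-year responder subgroups do bear on portal engagement, and Analysis Notes allow further robustness checks. But the subgroups do not restrict the primary sample, and the non-responder group may mix silent account holders with patients who have no account. The robustness checks are optional and do not name portal status.

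**Conclusion.** The omission is confirmed from the text: delivery is described only through the portal, and neither the enrolment rules nor the three criteria require an account. The consequence is conditional. If the pool included patients without accounts, the primary sample does not match its own label, and the estimate is pulled towards zero without bias between arms. How far depends on the unstated account share. Over an assumed 90% to 60%, and if 0.7 points applies to account holders, the power lost by not restricting runs from about 4 points (76.3% against 80.5%) to about 20 (43.1% against 63.4%). If 0.7 points is the all-patient average, there is no shortfall and restriction is purely a gain. The change is worthwhile on either reading, because it costs little and aligns the sample with the definition the SAP already uses.

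**What to change.** Add a fourth criterion to Analysis Notes, applied identically in both arms: the patient held an active portal account on the day before the questionnaire became available or, for a control, would have become available. Because this status precedes the questionnaire at the patient's first eligible appointment, assignment should not affect it, and the restricted comparison stays randomised.

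Report the account share by arm. As sensitivity analyses, give the estimate without this criterion and the estimate using account status at pre-randomisation in July 2022. The July date is further from any influence of assignment but drops patients who opened an account later and could have received the questionnaire, so it suits a sensitivity analysis better than the main definition.

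If the pool was already limited to portal users, one sentence saying so replaces all of this.

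The cost is one field from the health record and one line in the SAP. The downside is a smaller sample and a result that applies to portal users, which the existing definition already implies.

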Other Pre-specified Outcomes listed below include flu outcomes (diagnosis, complications) and COVID-19 vaccination. If there are any differences in these outcomes as a function of study arm, the mechanism would almost certainly be increased flu vaccination. Therefore, we will only run analyses on Other Pre-specified Outcomes for analyses above where there is a significant difference in flu vaccination.

1. Count of patients with a high confidence flu diagnosis

Patient received a flu diagnosis via a positive polymerase chain reaction (PCR)/antigen/molecular test (yes/no) during the 2022-23 flu season (from the patient’s study start date through April 30, 2023).

[Time Frame: Up to 8 months]

2. Count of patients with a "likely flu" diagnosis

Received a "high confidence flu" diagnosis (with positive PCR/antigen/molecular test) and/or "likely flu" diagnosis (as assessed via International Classification of Disease [ICD] codes or Tamiflu administration or positive PCR/antigen/molecular test) (yes/no) during the 2022-23 flu season (from the patient’s study start date through April 30, 2023).

Note that "likely flu" is a superset of the "high confidence flu" diagnoses.

[Time Frame: Up to 8 months]

3. Count of patients with flu complications

Diagnosed with flu-related complications (yes/no) from the patient's study start date through July 31, 2023.

[Time Frame: Up to 11 months]

4. ER visits

Number of ER visits from the patient's study start date through July 31, 2023.

[Time Frame: Up to 11 months]

5. Hospitalizations

Number of hospitalizations from the patient's study start date through July 31, 2023.

[Time Frame: Up to 11 months]

6. COVID-19 vaccination rates

Received at least one COVID-19 vaccination (yes/no) during the 2022-23 flu season (from the patient's study start date through April 30, 2023).

[Time Frame: Up to 8 months]

7. Count of patients with a flu vaccination during the 2022-2023 season

Patient received a flu vaccine (yes/no) during the 2022-23 flu season (from the patient's appointment date through April 30, 2023)

[Time Frame: Up to 8 months]

Additional Exploratory Analyses

1. Age and sex

People of different ages and sexes may react differently to the questionnaire. To test the relation between flu shots, age, and sex, we will run an OLS regression including binned patient age (18–24, 25–34, 35–44, 45–54, 65+), sex, and their interaction.

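### The significance gate on the other outcomes rests on a mechanism argument that is circular for season-long flu vaccination and unsupported for COVID-19 vaccination

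*Combined protocol and SAP*

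**What the plan says.** The section Other Pre-specified Outcomes lists seven outcomes: two definitions of flu diagnosis, flu complications, ER visits, hospitalizations, COVID-19 vaccination and season-long flu vaccination. One rule covers them all: "we will only run analyses on Other Pre-specified Outcomes for analyses above where there is a significant difference in flu vaccination". The reason given is causal: "If there are any differences in these outcomes as a function of study arm, the mechanism would almost certainly be increased flu vaccination". The sentence before it sets the scope: "Other Pre-specified Outcomes listed below include flu outcomes (diagnosis, complications) and COVID-19 vaccination". COVID-19 vaccination is therefore named, and season-long flu vaccination is not, although it sits under the same heading.

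The two outcomes at issue are:

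- Item 6: "Received at least one COVID-19 vaccination (yes/no) during the 2022-23 flu season", counted from the study start date to April 30, 2023.
- Item 7: "Count of patients with a flu vaccination during the 2022-2023 season", counted from the appointment date to April 30, 2023.

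The confirmatory analysis above the gate uses the primary outcome in Planned Analyses, a flu shot "between the day questionnaires became available for the patient's first scheduled flu-shot-eligible appointment and 7 days following the appointment", which is up to 21 days. The Power Analysis assumes about 82,500 patients per arm and two-sided alpha of .05: "This sample size allows 80% power to detect an increase in flu vaccination rates from 35% to 35.7" percent.

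**The concern.** A gate justified by mechanism is only as good as the mechanism is for each outcome behind it. Flu diagnosis and flu complications plausibly follow from vaccination, so the argument is at least coherent for them.

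Item 7 is not downstream of flu vaccination. It is flu vaccination, measured to a later date. Additional Exploratory Analyses, item 2, recognises that a patient may get more than one questionnaire in the season. Those later prompts, and any shot given more than 7 days after the first eligible visit, fall outside the primary window.

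For item 6 the plan offers no evidence that COVID-19 vaccination could move only through flu shots. The questionnaire reaches the patient and its answer reaches the clinician, so a direct effect in either direction is possible. That is conjecture, but the documents do not exclude it.

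At stake is whether, after a non-significant primary, the simple randomised comparisons for these two outcomes are run at all.

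**Working it through.** **1. Reproducing the plan's figure.** Inputs from Power Analysis: n = 82,500 per arm, control rate 35%, two-sided alpha .05, 80% power. With SE = sqrt(2 × p̄(1 − p̄)/n) and p̄ the mean of the two rates, the detectable difference is (1.96 + 0.84) × SE. At p̄ = 0.353, SE = 0.00235, which gives 0.0066. The detectable rate is 35.66%, which rounds to the stated 35.7%. The figure is reproduced. Taking 0.7 points as exact, power is Φ(0.007/0.00235 − 1.96) = 84.5%.

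**2. How often the gate closes.** P(closed) = 1 − power, treating the gate as the single confirmatory test:

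| True effect in the primary window (points) | P(closed), 82,500 per arm |
|---|---|
| 0 | 95% |
| 0.2 | 87% |
| 0.3 | 75% |
| 0.4 | 60% |
| 0.5 | 43% |
| 0.66 | 20% |
| 0.7 | 16% |

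The Analysis Notes narrow the sample by further criteria, and the documents do not say by how much. If 60,000 or 40,000 per arm remained (assumptions), the gate would close 28% or 46% of the time at 0.7 points.

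**3. What a closed gate costs item 7.** This was simulated with 100,000 replicates per scenario at 82,500 per arm. Each patient is vaccinated in the primary window (35% of controls), later, or not at all. Assumptions: a further 5%, 10% or 20% of controls are vaccinated later; the effect is split as shown; the season-long outcome contains the primary window. The last column is the probability that the primary is non-significant while the season-long test would have been significant.

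| Effect in window (points) | Effect later (points) | Season-long result lost |
|---|---|---|
| 0.7 | 0 | 4–7% |
| 0.35 | 0.35 | about 50% |
| 0.2 | 0.5 | 68–69% |
| 0 | 0.7 | 78–80% |

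The ranges cover the three late-vaccination rates.

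**4. What the trial could show on item 6.** The documents give no COVID-19 vaccination rate. At an assumed 10% to 30%, the 95% CI half-width is 1.96 × sqrt(2p(1 − p)/82,500): 0.29 points at p = 0.10 and 0.44 points at p = 0.30. If there were no effect on flu shots in the primary window, the gate would nevertheless stay closed 95% of the time.

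**5. The two flu-vaccination windows side by side.** The primary opens when the questionnaire becomes available, up to 14 days before the visit, and closes 7 days after it. Item 7 opens at the visit and closes on April 30, 2023. Items 1 to 6 all start at the study start date; only item 7 starts at the appointment. As written, item 7 therefore omits pre-visit shots that the primary counts, and it is not simply the primary with a later end. The simulation in step 3 describes item 7 with its start aligned to the primary.

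**The case against.** Gating secondary outcomes on the primary is a legitimate way to limit multiplicity. That stands as a general point, but the plan does not give multiplicity as its reason, and a non-confirmatory label would handle it for these two outcomes.

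A reader might infer that the mechanism claim is wrong for COVID-19 vaccination. The documents do not show that. The plan makes the claim expressly, and a COVID-19 shot given alongside a flu shot would fit it. The intervention is also narrow: one question about the flu shot and added text in an alert that already existed. The most that can be said is that the claim is asserted and not established.

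A reader might also infer that the gate amounts to selective reporting. It does not: the rule is public, and Project Status says no outcomes had been compared between arms when the document was uploaded. Testing under a rule fixed in advance is conditional, not selective.

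Nor would later flu shots go wholly unexamined. The repeat-exposure analysis is ungated, and the Analysis Notes allow a check that includes subsequent visits. However, the first groups patients by their number of eligible appointments and the second is optional. Neither replaces the randomised season-long comparison.

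It can be said that exempting only items 6 and 7 draws an uneven line: later vaccination could also move flu diagnoses, and ER visits and hospitalizations are not restricted to flu. That has some force. The distinction is that for items 1 to 5 vaccination is at least a coherent intermediate step, whereas for item 7 it is the outcome itself and for item 6 the link is unsupported.

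Finally, the gate refers to analyses in the plural and may apply analysis by analysis, subgroups included. The probabilities above describe the confirmatory comparison only.

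**Conclusion.** The point holds in limited form and is a desirable improvement. The primary analysis is not affected. The ground for the gate is circular for item 7 and unsupported for item 6, and a closed gate is not evidence of no effect.

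The cost depends on when any effect occurs. For item 7 it is small if the effect falls within the primary window and large only under assumed delayed effects, for which the documents give no figures. The late-vaccination rates, the COVID-19 rates, the reduced sample sizes and every effect size other than 0.7 points are assumptions. The case for item 7 is the stronger of the two; that for item 6 rests on the missing justification.

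**What to change.** Amend the gating sentence so that it no longer covers items 6 and 7, and drop the mechanism claim for them. Report each with its between-arm estimate and 95% CI whatever the primary result, labelled non-confirmatory.

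Start item 7 on the day the questionnaire became available, or would have become available for controls, so that it contains the primary window and pre-visit shots are not lost. Make the change before outcomes are compared between arms; if that comparison has already been made, say so when reporting.

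The cost is a short SAP edit and two regressions on outcomes already defined. The downside is two more non-confirmatory estimates to interpret after a null primary. Primary alpha is unaffected.

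### Season flu vaccination (Outcome 7) starts counting at the visit, so it leaves out pre-visit shots that the primary outcome counts

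*Combined protocol and SAP*

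**What the plan says.** The primary outcome (SAP, Planned Analyses) is defined as "Patient received a flu vaccine (yes/no) between the day questionnaires became available" for the first eligible appointment and 7 days after that appointment. On timing, the same section says: "Questionnaires were available 14 days prior to the appointment date for appointments scheduled at least 14 days in advance". For later bookings, the questionnaire opens on the booking day.

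The enrollment conditions that close the Methods section require that, according to the EHR, "they have not yet received a flu shot at the time the questionnaire becomes available". For controls, the condition applies at the time it would have become available.

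Item 7 of Other Pre-specified Outcomes is titled "Count of patients with a flu vaccination during the 2022-2023 season", but its window runs from the patient's "appointment date through April 30, 2023". Items 1, 2 and 6 run from the patient's "study start date through April 30, 2023". Items 3 to 5 use the same start and end on July 31, 2023. The introduction to that section sets a gate: "we will only run analyses on Other Pre-specified Outcomes for analyses above where there is a significant difference in flu vaccination".

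Nothing in the documents explains why item 7 alone starts at the appointment.

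**The concern.** A season-long outcome should contain the short-window outcome it extends. This one does not. Enrolled patients have no recorded shot when the questionnaire opens, so a shot between that day and the visit comes after the intervention has begun. The primary counts it and Outcome 7 drops it.

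Applying the same rule in both arms does not remove the problem, because the questionnaire is delivered before the visit and may itself change when people are vaccinated. It could prompt some to get a shot early, or lead others to wait for the visit. In the first case Outcome 7 understates the season effect, and in the second it overstates it.

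What is at stake is how a significant primary result is interpreted. The natural use of a season outcome is to ask whether the gain lasts or whether controls catch up later. If Outcome 7 comes out smaller than the primary, the two reported differences cannot show whether controls caught up after day +7 or whether pre-visit shots were simply left out.

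**Working it through.** **Windows.** Lead time from questionnaire to visit is 14 days for visits booked at least 14 days ahead, and 0 to 13 days otherwise (Planned Analyses). Adding the 7 days after the visit gives a primary window of 7 to 21 days, which reproduces the stated time frame of up to 21 days. The part of that window before Outcome 7 starts is:

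- lead 0: 0 of 7 days
- lead 7: 7 of 14 days (50%)
- lead 14: 14 of 21 days (67%)

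**Arm differences.** Assume at most one counted shot per patient per season. For questionnaire minus control, let

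- dP = difference in shots from the questionnaire-available day to the day before the visit
- dV = difference from the visit to day +7
- dL = difference from after day +7 to April 30, 2023

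Then:

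- Primary = dP + dV
- Full season = dP + dV + dL
- Outcome 7 as written = dV + dL = full season - dP
- Outcome 7 - primary = dL - dP
- Season outcome with the primary's start - primary = dL

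Only the last line isolates what happens after day +7.

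**Illustration.** The documents give no pre-visit vaccination figures, so the values of dP are assumptions. Set the primary difference at the design effect, 35.7% - 35% = 0.70 percentage points (Power Analysis), and assume Outcome 7 shows 0.50. Then dV = 0.70 - dP, dL = 0.50 - dV = dP - 0.20, and full season = 0.50 + dP.

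| dP | dV | dL | Full season |
|---|---|---|---|
| +0.20 | 0.50 | 0 | 0.70 |
| +0.05 | 0.65 | -0.15 | 0.55 |
| 0 | 0.70 | -0.20 | 0.50 |
| -0.05 | 0.75 | -0.25 | 0.45 |
| -0.20 | 0.90 | -0.40 | 0.30 |

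All five rows give the same two reported results. At one end there is no later catch-up by controls; at the other it is 0.40 points. For a given season effect, each 0.1 point of dP moves Outcome 7 by 0.1 point the other way.

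**Effect of the gate.** If the questionnaire only defers shots to the visit (for example dP = -0.20, dV = +0.20), the primary difference is 0. At two-sided alpha .05 the overall gate then stays closed about 95% of the time. The error therefore matters mainly when the primary is truly different, and it concerns the size of the season effect.

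**Containment after correction.** The last primary window closes on 4/8/23 (Project Status), before April 30. With the same start date, the season window contains the primary window for every patient.

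**The case against.** The strongest reply is that no information is lost. The two windows overlap at the visit, and together they cover the whole period from the questionnaire to April 30. A patient's full-season status is yes on either outcome. With one shot per patient, the pre-visit shots are exactly those patients who are yes on the primary and no on Outcome 7. That is correct: the analysts can recover everything from patient-level data. But the plan does not specify that combination, and a reader of the two reported differences cannot reconstruct it.

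Second, Outcome 7 is a valid randomized comparison of shots from the visit onward, so the fault is a mismatch between title and window. This is fair as a description. It also means that the outcome as titled is not the one that would be estimated.

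Third, the sizes are assumed, and the outer rows of the table need combinations that nothing in the documents supports. This stands; neither size nor direction of the error can be shown.

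Fourth, the documents do not define the study start date, so items 1 to 6 are weak evidence of a different start. This also stands, and the point does not depend on them; the contrast with the primary is enough.

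**Conclusion.** The inconsistency is real. As written, Outcome 7 omits 0 to 14 days of post-questionnaire follow-up that the primary includes, and it misclassifies patients vaccinated in that interval relative to its own title. The gap is zero for same-day bookings and 14 days for visits booked 14 or more days ahead.

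The resulting error in the season effect equals the arm difference in pre-visit shots, with sign reversed. Its size and direction are unknown from the documents. The algebra rests on one counted shot per patient.

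Severity is minor. Outcome 7 is a gated, non-primary outcome, and the confirmatory test, alpha and sample size do not change.

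**What to change.** Redefine the Outcome 7 window to run from the day the questionnaire became available for the patient's first flu-shot-eligible appointment (or, for controls, the day it would have become available) through April 30, 2023. Name that day explicitly rather than relying on the undefined study start date. Leave the gate unchanged.

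The cost is one phrase. The questionnaire-available date and the vaccination dates are already required for the primary in both arms. For a 9/1/22 visit with a 14-day lead, the window would run from 8/18/22, which is 255 days instead of 241, or about 8.4 months instead of 7.9. The stated time frame of up to 8 months then holds only by rounding. It can stay on that basis, or be reworded in the same edit.

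Project Status says "final outcomes data were not pulled or reviewed prior to uploading this document", so on the plan's own account the change could be made before results were known. If outcome data have since been seen, report both definitions and disclose when the change was made.
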